Each item on the 36-item short-form health survey will be answered by the patients (on scales of 1 to 3, 1 to 5, or 1 to 6). Some of those answers will then be re-coded so that across all questions, a higher score will indicate a better health state. Questions 3a-3j, ,9a, 9d, 9e, 9h, 11b, 11d will be scored as recorded; the other questions will have the scores transformed as shown in the

Table 1.

The raw score for the following 8 scales will be calculated by summing the scores (either original or re-coded depending on the question) for the set of questions listed in **Table 2** if all of the questions within that scale are answered. If < 50% of the questions within a scale is answered, then the raw score will not be calculated.

Table 1

| SF-36v2: Re-code | | | | | | |
|---|------------------------------------|-----|-----|-----|-----|-----|
| Question | Original code and re-code response | | | | | |
| Question number: 1 | | | | | | |
| Original response | 5 | 4 | 3 | 2 | 1 | |
| Re-coded response | 5 | 4.4 | 3.4 | 2 | 1 | |
| Questions numbers: 6 | | | | | | |
| Original response | 1 | 2 | 3 | 4 | 5 | |
| Re-coded response | 5 | 4 | 3 | 2 | 1 | |
| Questions numbers: 4a-4d, 5a-5c, 9b, 9c, 9f, 9g, 9i, 10, 11a, 11c | | | | | | |
| Original response | 5 | 4 | 3 | 2 | 1 | |
| Re-coded response | 1 | 2 | 3 | 4 | 5 | |
| Question number: 7 | | | | | | |
| Original response | 1 | 2 | 3 | 4 | 5 | 6 |
| Re-coded response | 6 | 5.4 | 4.2 | 3.1 | 2.2 | 1 |
| Question number: 8 (if question number 7 is answered) | | | | | | |
| Original response to #8 | 1 | 1 | 2 | 3 | 4 | 5 |
| Original response to #7 | 1 | 2-6 | 1-6 | 1-6 | 1-6 | 1-6 |
| Re-coded response | 6 | 5 | 4 | 3 | 2 | 1 |

|  cros nt | Forms | | | |
|---|--------------|------------------------------------|----------------|----------|
| | Title | Statistical Analysis Plan Template | | |
| | Code | Version | Effective Date | Page |
| | FRM_ST03_032 | 01 | 23 Apr 2015 | 22 of 31 |

| SF-36v2: Re-code | | | | | | |
|---|------------------------------------|------|-----|------|---|--|
| Question | Original code and re-code response | | | | | |
| Question number: 8 (if question number 7 is NOT answered) | | | | | | |
| Original response | 1 | 2 | 3 | 4 | 5 | |
| Re-coded response | 6 | 4.75 | 3.5 | 2.25 | 1 | |

Table 2

| SF-36v2: Scales | |
|---------------------------|--------------------|
| Scales | Questions |
| Physical functioning (PF) | 3a to 3j |
| Role – physical (RP) | 4a to 4d |

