| Bodily pain (BP) | 7, 8 |
| General health (GH) | 1, 11a to 11d |
| Vitality (VT) | 9a, 9e, 9g, 9i |
| Social functioning (SF) | 6, 10 |
| Role - emotional (RE) | 5a to 5c |
| Mental health (MH) | 9b, 9c, 9d, 9f, 9h |

If $\geq 50\%$ but not all of the questions are answered on a domain, first the non-missing questions are recoded (if necessary) and then summed. An average score is calculated for those non-missing scores and that average score is filled in as the score to be used for the value of the missing questions. The raw score is then calculated as the sum of all the question scores. For example, for the VT scale, if questions 9a, 9e, and 9g are answered but question 9i is missing, the algorithm will proceed as shown in **Table 3** from left to right:

Table 3

| SF-36v2: Algorithm for unanswered questions | | | | | |
|---|---------------------------|--------------------------|--|--|--|
| Question | Patient recorded response | Response after re-coding | | Average is filled in for missing responses | |
| 9a | 1 | 5 | Average of non-missing scores = $(5+3+5)/3 = 4.33333$. | 5 | Raw score = $5+3+5+4.3333... = 17.33333...$ |
| 9e | 3 | 3 | | 3 | |
| 9g | 5 | 5 | | 5 | |
| 9i | Missing | Missing | | 4.33333... | |

After the raw score is calculated, the raw score is then converted into a transformed scale score (on a scale of 0 to 100) using the following transformation:

| Forms | | | | |
|--------------|--|------------------------------------|----------------|----------|
| Title | | Statistical Analysis Plan Template | | |
| Code | | Version | Effective Date | Page |
| FRM_ST03_032 | | 01 | 23 Apr 2015 | 23 of 31 |

$$\text{Transformed scale score} = \frac{\text{Total raw score} - \text{Lowest possible raw score}}{\text{Possible raw score range}} \times 100$$

The transformed scale scores will then be standardised using the following formula for the z-score transformation:

$$z\text{-score} = \frac{\text{Transformed scale score} - \text{Mean of General US population}}{\text{Standard deviation of General US population}}$$

For example, a VT total raw score of 17.33333 would be transformed as follows:

$$\text{VT transformed scale score} = \frac{17.33333 - 4}{16} \times 100 = 83.3333125$$

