As shown in Table 4, the lowest possible VT score equals 4 and the possible VT total raw score range equals 16. This transformation converts the lowest and highest possible raw scores to 0 and 100, respectively. Scores between these values represent the percentage of the total possible score achieved.

When based on the 1998 US general population, the VT z-score is as follows:

$$\text{VT z-score} = \frac{83.3333125 - 58.41968}{20.87823}$$

The lowest possible raw score, possible raw score range, mean and standard deviation for each scale are shown in **Table 4**.

Table 4

| Lowest possible raw score and range, and means and standard deviations for deriving the z-scores for the scales of the SF-36v2 ACUTE form | | | | |
|---|---------------------------|--------------------------|----------|--------------------|
| Scale | Lowest possible raw score | Possible raw score range | Mean | Standard deviation |
| PF | 10 | 20 | 82.62455 | 24.43176 |
| RP | 4 | 16 | 82.65109 | 26.19282 |
| BP | 2 | 10 | 73.86999 | 24.00884 |
| GH | 5 | 20 | 70.78372 | 21.28902 |
| VT | 4 | 16 | 58.41968 | 20.87823 |
| SF | 2 | 8 | 85.11568 | 23.24464 |
| RE | 3 | 12 | 87.50009 | 22.01216 |
| MH | 5 | 20 | 75.76034 | 18.04746 |

| Forms | | | |
|--------------|--|------------------------------------|----------------|
| Title | | Statistical Analysis Plan Template | |
| Code | | Version | Effective Date |
| FRM_ST03_032 | | 01 | 23 Apr 2015 |
| | | | 24 of 31 |

The physical and mental component raw scores are composed of a combination of the 8 domain z-scores and these will be calculated based on each domain scale z-score multiplied by a constant provided in **Table 5**, and then add the 8 scales together.

To illustrate, a portion of the formula for aggregating scales when estimating an aggregate physical and mental component score are as follows:

$$\text{Aggregate PCS} = (\text{PF z-score} \times 0.42402) + \dots + (\text{GH z-score} \times -0.22069)$$

$$\text{Aggregate MCS} = (\text{PF z-score} \times -0.22999) + \dots + (\text{MH z-score} \times 0.48581)$$

Note: if any of the 8 domain z-score is missing the aggregate PCS and MCS will be missing.

The T-scores for the 8 scale scores will be calculated by multiplying the scale z-scores by 10 and adding 50.

To illustrate, a portion of the formula for transforming domain scale z-scores to T-scores:

$$\text{PF T-score} = 50 + (\text{PF z-score} \times 10)$$

$$\text{MH T-score} = 50 + (\text{MH z-score} \times 10)$$

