The physical and mental component T-scores will then be calculated by multiplying the component raw scores by 10 and adding 50.

The formulas for computing the norm-based T-score for each component summary measure are:

$$\text{PCS T-score} = 50 + (\text{Aggregate physical component score} \times 10)$$

$$\text{MCS T-score} = 50 + (\text{Aggregate mental component score} \times 10)$$

Table 5

| SF-36v2: Scale constants used to calculate component scores | | |
|---|---------------------------|-------------------------|
| Scale | Physical health component | Mental health component |
| PF | 0.42402 | -0.22999 |
| RP | 0.35119 | -0.12329 |
| BP | 0.31754 | -0.09731 |
| GH | 0.24954 | -0.01571 |
| VT | 0.02877 | 0.23534 |
| SF | -0.00753 | 0.26876 |
| RE | -0.19206 | 0.43407 |
| MH | -0.22069 | 0.48581 |

The responses to the SF-36v2 at Visit 9 (Day 28) will also be categorized as improved, worsened and stable based on the changes from baseline in T-score. The criteria for a MCID (Ware et al, 2007) will be used to assign a visit response for each score (see **Table 6**). The T-scores will be based on the 1998 US general population survey as reported in Ware et al, 2007. At follow up visit, the criteria that will be used to assign a visit response to the changes from baseline will be based on the MCIDs shown in **Table 6**.

Only patients with a non-missing score at both baseline and at Visit 9 (Day 28) will be considered eligible for categorization.

| Forms | | | | |
|--------------|--|------------------------------------|----------------|----------|
| Title | | Statistical Analysis Plan Template | | |
| Code | | Version | Effective Date | Page |
| FRM_ST03_032 | | 01 | 23 Apr 2015 | 25 of 31 |

Table 6

| Response Categories | | | | |
|---------------------|--------------|--------------|-----------|--|
| Visit response | | | | |
| Score | Improved | Worsened | Stable | |
| PCS | $\geq + 3.1$ | $\leq - 3.1$ | Otherwise | |
| MCS | $\geq + 3.8$ | $\leq - 3.8$ | Otherwise | |
| PF | $\geq + 3.5$ | $\leq - 3.5$ | Otherwise | |
| RP | $\geq + 3.2$ | $\leq - 3.2$ | Otherwise | |
| BP | $\geq + 4.5$ | $\leq - 4.5$ | Otherwise | |
| GH | $\geq + 5.7$ | $\leq - 5.7$ | Otherwise | |
| VT | $\geq + 5.5$ | $\leq - 5.5$ | Otherwise | |
| SF | $\geq + 5.0$ | $\leq - 5.0$ | Otherwise | |
| RE | $\geq + 3.8$ | $\leq - 3.8$ | Otherwise | |
| MH | $\geq + 5.5$ | $\leq - 5.5$ | Otherwise | |

EuroQol-5 Dimensions Health Questionnaire (EQ-5D)

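### The SF-36v2 recode rule and the worked example in SAP 7.3 score Vitality items 9a and 9g in opposite directions, so the same answers can be classed Improved or Worsened

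*SAP*

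**What the plan says.** All of this is in SAP section 7.3, in the SF-36v2 text and Tables 1 to 6.

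- **Rule.** After recoding, a higher value is to mean better health on every item. The text states "Questions 3a-3j, ,9a, 9d, 9e, 9h, 11b, 11d will be scored as recorded" and sends all other questions to Table 1.
- **Table 1.** The block headed "Questions numbers: 4a-4d, 5a-5c, 9b, 9c, 9f, 9g, 9i, 10, 11a, 11c" maps 5, 4, 3, 2, 1 to 1, 2, 3, 4, 5. Items 9g and 9i are therefore reversed.
- **Table 3.** This illustrates how a missing Vitality item is filled. The text says "the algorithm will proceed as shown in" that table. Its first row reads "9a | 1 | 5 | Average of non-missing scores", so a recorded 1 on 9a becomes 5. Item 9e goes from 3 to 3, 9g from 5 to 5, and 9i is missing.
- **Use of the scores.** Day 28 responses "will also be categorized as improved, worsened and stable based on the changes from baseline in T-score". Table 6 sets the VT threshold at 5.5 T-points either way.

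**The concern.** Under the rule, 9a keeps its recorded value and 9g is reversed. Under Table 3, 9a is reversed and 9g keeps its recorded value. A programmer cannot follow both. The documents do not show which is right, because the item wording is not printed and no SF-36 scoring manual is named as governing the recode.

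At least one instruction gives these two items the wrong sign in VT, and through VT in the mental component score (MCS) and, slightly, the physical component score (PCS). With planned cohorts of four, one misclassified patient is 25% of a cohort. The independent programming in SAP 9.1 would expose the problem only if the two programmers happened to follow different instructions.

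Table 3 tests only 9a and 9g, since 9e sits at the midpoint and 9i is missing. No other item is shown to be wrong. The same as-recorded list and Table 1 block do, however, supply items to PF, RP, GH, SF, RE and MH, so those items should be checked too.

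**Working it through.** **Inputs (SAP 7.3).** VT items are 9a, 9e, 9g and 9i (Table 2). Lowest raw score 4, range 16, mean 58.41968, SD 20.87823 (Table 4). T = 50 + 10z. VT weights are 0.02877 for PCS and 0.23534 for MCS (Table 5). Thresholds are VT 5.5, MCS 3.8 and PCS 3.1 (Table 6).

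**1. The SAP's example (9a=1, 9e=3, 9g=5, 9i missing).** The stated figures reproduce only with the Table 3 recode.

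| | Table 3 | Written rule and Table 1 |
|---|---|---|
| Recoded 9a, 9e, 9g | 5, 3, 5 | 1, 3, 1 |
| Mean, used to fill 9i | 13/3 = 4.333 | 5/3 = 1.667 |
| Raw score | 17.333 | 6.667 |
| Transformed, (raw - 4)/16 × 100 | 83.33 | 16.67 |
| z | 1.193 | -2.000 |
| T | 61.9 | 30.0 |

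The gap is 31.9 T-points. The SAP carries 17.33333 and 83.3333125 into its later formulas, so the Table 3 values are not a text-extraction fault.

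**2. Size of one raw point.** (1/16 × 100)/20.87823 × 10 = 2.994 T-points.

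**3. Change from baseline.** Take a baseline of all 3s (raw 12 under either instruction) and hold 9e and 9i at 3. This baseline is an illustration.

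- Day 28 with 9a=2, 9g=4. Rule: 2+3+2+3 = 10, change -2, T -5.99, Worsened. Table 3: 4+3+4+3 = 14, change +2, T +5.99, Improved.
- Day 28 with 9a=1, 9g=5, the recorded values Table 3 itself prints. Rule: raw 8, T -11.97. Table 3: raw 16, T +11.97.

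**4. General form with 9e and 9i unchanged.** Let d be the change in the recorded answer. The raw change is d9a - d9g under the rule and d9g - d9a under Table 3: equal size, opposite sign. A net shift of one is 2.99 T-points, Stable under both. A net shift of two or more is at least 5.99 and switches the class.

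**5. With all four items free.** Over all possible pairs of complete baseline and Day 28 answers, 25.7% switch between Improved and Worsened if only 9a and 9g differ between the instructions. This counts answer patterns and is not a patient rate.

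**6. Component scores.** For the two-point move, MCS changes by 0.5987 × 0.23534 × 10 = 1.41 in either direction (gap 2.82), and PCS by 0.5987 × 0.02877 × 10 = 0.17. Neither crosses its threshold through VT alone. A net shift of six would move MCS by 6 × 2.994 × 0.23534 = 4.23, past 3.8. The largest possible net shift, eight, moves PCS by only 8 × 2.994 × 0.02877 = 0.69.

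**The case against.** Table 3 exists to show how a missing answer is filled, not to define the recode, and it prints one value per item. Reading it as a full mapping (9a reversed throughout, 9g unchanged throughout) is an inference. That is fair, but the inference is the natural one, and neither the SAP's own example nor the 9a=1, 9g=5 case relies on any unprinted value beyond the midpoint, which is 3 under either coding.

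The exact sign reversal requires 9e and 9i to be unchanged, a narrow set of patterns. That also stands; without the condition, some patients switch class and others do not.

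No table title in SAP 9.3 names the Improved/Worsened/Stable categories, and the shells are not available here. Even so, VT change from baseline is to be summarised, and its sign is what is in doubt.

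The impact is limited and probably recoverable. No protocol objective rests on SF-36v2, and SAP 4.1 lists all endpoint data, so scores could be recomputed if item responses are included. Protocol 6.7.13 points to a Procedure Manual that might settle the coding. These points bear on severity; they do not reconcile the two instructions.

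**Conclusion.** The contradiction is real and internal to the SAP. It reverses the contribution of 9a and 9g to Vitality: 31.9 T-points on the SAP's own example, and a switch between Improved and Worsened for any net shift of two or more categories when 9e and 9i do not change. The size of the change result assumes the Table 3 recode extends to all response values in the obvious way. Which instruction is correct cannot be decided from the documents.

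The SAP's arithmetic is sound; the scoring definition is inconsistent. It should be fixed, but it touches only a descriptive endpoint.

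Two smaller slips sit in the same section. The PCS illustration attaches -0.22069 to GH, whereas Table 5 has "GH | 0.24954 | -0.01571" and gives -0.22069 to MH. Table 5 is the operative source, so this is a labelling error. The text also says the standard form is used, while the Table 4 caption refers to the acute form. Separately, Table 1 prints the same mapping twice, once under "Questions numbers: 6" and once for the longer list. That is not an error in itself, only a further reason to recheck the table.

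**What to change.** 1. Before scoring, check every recoded SF-36v2 item against the printed questionnaire, the eCRF codes and the scoring manual for the form used. Consult the Procedure Manual as well.
2. Amend either the written rule and Table 1, or Table 3, so that the rule reproduces the example.
3. Add a program test: the recorded answers in the reconciled example must return its stated raw score (17.333 if Table 3 stands).
4. In the PCS illustration, relabel the -0.22069 term as MH. Name one SF-36v2 form and confirm that the Table 4 norms belong to the form administered.
5. If scoring has already been run, establish which recode was programmed and rescore if necessary.

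The cost is a short SAP correction and one scoring-program check. No new data are needed and patients are not affected.

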If 15b = 3, then 15c should be recoded to missing.

* Response choice 6 indicates that the person does not perform the activity because of non-vision related problems.
If this choice is selected, the item is coded as missing.

Step 2

The re-coded scores are grouped into 12 categories as shown in the table below, and the mean of the non-missing values in each category represents the subscale score for that category.

| Scale | Number of Questions | Question Numbers to be Averaged for Subscale Score (after re-coding) |
|---------------------|---------------------|--|
| General Health | 1 | 1 |
| General Vision | 1 | 2 |
| Ocular Pain | 2 | 4, 19 |
| Near Activities | 3 | 5, 6, 7 |
| Distance Activities | 3 | 8, 9, 14 |
| Vision-Specific: | | |
| Social Functioning | 2 | 11, 13 |
| Mental Health | 4 | 3, 21, 22, 25 |
| Role Difficulties | 2 | 17, 18 |
| Dependency | 3 | 20, 23, 24 |
| Driving | 3 | 15c, 16, 16a |
| Color Vision | 1 | 12 |
| Peripheral Vision | 1 | 10 |

Step 3

The overall composite score is calculated as the mean of 11 subscale scores that were derived in Step 2, excluding the “General Health” subscale score. If not all subscale scores are calculated due to missing values, the mean of the available subscale scores will be taken.

SF36™ Health Survey Version 2 (SF-36v2)

|  cros nt | | Forms | | | |
|--|--|------------------------------------|---------|----------------|----------|
| | | Statistical Analysis Plan Template | | | |
| | | Code | Version | Effective Date | Page |
| | | FRM_ST03_032 | 01 | 23 Apr 2015 | 21 of 31 |

The SF-36 is a multi-purpose, short-form health survey with only 36 questions yielding 8 health domain scales and 2 psychometrically based physical and mental component summary measures. The standard form of the SF-36v2 will be used. The question number 2 will not be used to score any of the 8 health domain scales or 2 summary measures because it is not applicable.

The 8 health domain scales are referred to as the ‘Physical Functioning (PF)’, ‘Role- Physical (RP)’, ‘Bodily Pain (BP)’, ‘General Health (GH)’, ‘Vitality (VT)’, ‘Social Functioning (SF)’, ‘Role-Emotional (RE)’, and ‘Mental Health (MH)’ scales. The 2 summary measures are referred to as the physical component score (PCS) and mental component score (MCS).

The methods of SF-36v2 scoring, handling of missing values, z- and T-score transformations are provided below.

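### SAP 7.3 contradicts itself twice on SF-36v2 scoring: the illustrated PCS line pairs General Health with Table 5's Mental Health constant, and the norm table names a different form from the one to be used

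*SAP*

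**What the plan says.** All of this is in SAP 7.3, in the part on the SF-36v2.

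- **Scoring rule.** The component raw scores are "calculated based on each domain scale z-score multiplied by a constant provided in" Table 5, and the eight products are then added.
- **Illustration.** Two lines follow, introduced by "To illustrate, a portion of the formula for aggregating scales when estimating an aggregate physical and mental component score". Each prints a first and a last term with an ellipsis between them. The PCS line ends with "GH z-score} \times -0.22069" (GH z-score times -0.22069). The line for the mental component score (MCS) ends with the MH z-score times 0.48581.
- **Table 5** (columns: physical constant, then mental constant). The GH row reads "GH | 0.24954 | -0.01571" and the MH row reads "MH | -0.22069 | 0.48581".
- **Form.** The section opens with "The standard form of the SF-36v2 will be used".
- **Norms.** The title of Table 4 describes its contents as "means and standard deviations for deriving the z-scores for the scales of the SF-36v2 ACUTE form". The text refers to the 1998 US general population without naming a form.
- **Use.** Component scores become T-scores as 50 plus 10 times the aggregate. Table 6 classes the Day 28 change from baseline as improved, worsened or stable, with cut-offs of 3.1 points either way for PCS and 5.7 for GH.

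**The concern.** For GH in the PCS, the printed line and Table 5 disagree in sign as well as size. A programmer who followed the printed term would make better general health lower the physical score, and the error could move a patient across the PCS cut-off in Table 6. In a planned cohort of four, one reclassified patient is 1/4 = 25% of the cohort.

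The second conflict reaches further but is milder. The Table 4 means and SDs standardise all eight scales, so they feed every scale T-score, both component scores and every Table 6 category. If they belong to a form other than the one patients completed, each of those values is on the wrong scale.

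**Working it through.** **Step 1. Reproduce the SAP's worked figure.** The vitality (VT) example uses a raw score of 17.33333, a lowest score of 4 and a range of 16:

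(17.33333 - 4) / 16 x 100 = 83.3333125, as printed.

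The SAP sets up the z-score but does not evaluate it: (83.3333125 - 58.41968) / 20.87823 = 1.193. The transformation steps work as written.

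**Step 2. Look up each illustrated constant in Table 5.**

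| Illustrated term | Printed | Table 5 | Match |
|---|---|---|---|
| PCS, PF | 0.42402 | 0.42402 | yes |
| PCS, GH | -0.22069 | 0.24954 | no |
| MCS, PF | -0.22999 | -0.22999 | yes |
| MCS, MH | 0.48581 | 0.48581 | yes |

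The PF row in Table 5 is "PF | 0.42402 | -0.22999". The one failing term matches exactly if its label is read as MH. MH is the last row of Table 5 and the last term of the parallel MCS line.

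**Step 3. Size, if the printed term were coded.** Inputs: GH SD 21.28902 (Table 4), the two constants above, and the T-score multiplier of 10.

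GH gain of 20 points on the 0-100 scale:
- z change = 20 / 21.28902 = 0.939
- Table 5: 0.939 x 0.24954 x 10 = +2.34
- Printed line: 0.939 x (-0.22069) x 10 = -2.07
- Gap between readings: 2.34 + 2.07 = 4.4 points

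GH gain at the Table 6 cut-off of 5.7 T-score points (z change 0.57):
- Table 5: 5.7 x 0.24954 = +1.42
- Printed line: 5.7 x (-0.22069) = -1.26
- Gap: 2.68 points, below the 3.1 cut-off for PCS

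**Step 4. Can a category change?** Suppose all eight scales rise by 0.5 SD.
- The Table 5 physical constants sum to 0.95078, so PCS rises by 10 x 0.5 x 0.95078 = 4.75, which is improved.
- If GH takes -0.22069 and MH keeps its own constant, the sum is 0.95078 - 0.24954 - 0.22069 = 0.48055. PCS rises by 2.40, which is stable.

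So a category can change under that reading.

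**Step 5. What the norms can and cannot do.** For a scale with transformed scores X0 at baseline and X1 at Day 28:

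T-score change = 10 x [(X1 - mean)/SD - (X0 - mean)/SD] = 10 x (X1 - X0) / SD.

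The mean cancels, and a positive SD only rescales. A different set of norms would therefore change the size of each scale's T-score change in proportion to 1/SD. It could not reverse the direction of that change, or of that scale's contribution to PCS. Means still affect the baseline and Day 28 levels. The documents give no second set of norms, so the size of any mismatch cannot be computed from them.

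**The case against.** The strongest reply is that the SAP does not score GH negatively. Table 5 is the operative rule. The faulty line is labelled an illustration and shows only two of eight terms, so PCS cannot be computed from it without Table 5. The other three constants are right and the MCS line ends with MH, so the slip identifies itself. A wrong result requires a programmer to override the GH row from the example. SAP 9.1 also requires independent programming of tables with comparison of results. This reply largely stands, and it limits the point to a contradiction that needs correcting. It does not remove the point: an illustration exists to show how the rule is applied, and two programmers working from one document can share its error.

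Three stronger readings are tempting, and the documents support none of them.

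- A reader might infer that the planned PCS will fall when general health improves. That follows only if the printed term is coded in place of Table 5.
- A reader might infer that the acute-form label makes the T-scores wrong, or contributes to the sign reversal. Step 5 shows that it cannot reverse a sign. The table title, the values or the named form could each be the item in error.
- A reader might take a GH change of about 14 points as enough to shift PCS by 3.1. The figure is 3.1 x 21.28902 / (10 x 0.47023) = 14.0, where 0.47023 is the distance between the two constants. It is the change at which the two readings differ by 3.1, not a movement in any patient's PCS.

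**Conclusion.** Both contradictions are real and stand in the current SAP text.

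The PCS line is very probably a mislabelled last term. Its consequence is conditional on the printed term being coded: a 4.4-point gap for a 20-point GH gain, and 2.68 points at the SAP's own GH threshold, against a PCS cut-off of 3.1. The 20-point gain is a chosen example, not a figure from the plan.

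The form conflict is unresolved on the documents. Any effect would be a rescaling in proportion to 1/SD, of unknown size.

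The impact is limited. The SF-36v2 is listed among the other endpoints (SAP 3.7.2) and summarised descriptively. The primary endpoints are safety parameters (SAP 3.5.1), and no SF-36v2 result enters the dosing or stopping rules in SAP 3.1. The correction is worth making because either conflict can change a reported T-score or a Table 6 category.

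**What to change.** Issue an SAP erratum for section 7.3 that:

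1. changes the last term of the illustrated PCS line to MH z-score x -0.22069;
2. states that Table 5 governs wherever an illustration differs from it;
3. confirms which SF-36v2 form was administered, and makes the form statement and Table 4 agree with it, by correcting the values, the table title or the form name as needed.

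Then check the PCS and MCS program line by line against Table 5.

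The same check should cover the Table 3 example, a separate conflict in this section. The example recodes item 9a from 1 to 5 and leaves 9g at 5. The text before Table 1 scores 9a as recorded, and Table 1 recodes 9g from 5 to 1. Under those rules the example's raw score is 1 + 3 + 1 + 1.67 = 6.67, not 17.33.

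The cost is an erratum and a program check, with a rerun of the SF-36v2 output if the code or the norms change. No new data are needed.
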